## Children

1. \* Check all of the childrens categories that apply to the study:

45 Research involving no greater than minimal risk to children, with adequate provisions for soliciting the assent of the CFR children and permission of their parents or guardians, as set forth in Sec. 46.408  
46.404

45 Research involving greater than minimal risk but presenting the prospect of direct benefit to individual CFR participants  
46.405

45 Research involving greater than minimal risk and no prospect of direct benefit to individual participants, but likely to yield CFR generalizable knowledge about the participant's disorder or condition  
46.406

45 Research not otherwise approvable which presents an opportunity to understand, prevent or alleviate a serious problem CFR affecting the health or welfare of children. (Research in this category must be reviewed and approved by the Secretary 46.407 of the Department of Health & Human Services)

2. \* Will this study involve participants who could be wards of the state:

Yes

No

3. \* Describe how children will be assented to participate in the study:

Not applicable - this study is recruiting newborn infants only

4. \* Describe how you plan to obtain permission of parents or guardians:

Parents of stable infants receiving non-invasive ventilation will be approached in their private single patient NICU rooms and presented with layman-term information about the study. They will be given a copy of the consent form, all of their questions will be answered and they will have the opportunity to take the information home to review.

ID: HM20005575

[View: SF - Children: Direct Benefit \[45 CFR 46.405\]](#)

## Children: Direct Benefit [45 CFR 46.405]

1. \* Explain briefly how the risk is justified by the anticipated benefit to participants:

While both modes of non-invasive ventilation are currently approved and used in the US and in the VCU NICU, it is not known which may be better. Hence, there is a possibility that one mode may be inferior to the other. Currently, a clinician picks one mode and then watches for clinical signs to determine if they picked the right one. By participating in this study, the subject gets exposed to both in a brief period of time, and the efficacy and superiority of one over the other can be assessed. In normal care, this side by side assessment is not done.

2. \* Explain briefly how the relation of the anticipated benefit to the risk is at least as favorable to the participants as that presented by available alternative approaches:

The alternative approach is to not participate. Study participants will be far more intensely monitored for how the ventilation mode is working than non-participants. Non-participants depend on nursing observation (a nurse may have 1-2 other patients) and historic data from the monitor. Participants will have an investigator watching their respiratory status continuously for four hours on each mode, so be better able to assess which one is better for the subject. This information will be shared with the clinical team who may use it to potentially select a better mode of non-invasive ventilation for that patient.

ID: HM20005575

[View: SF - Pregnant Women, Fetuses, Neonates and Post-Delivery Material](#)

## Pregnant Women, Fetuses, Neonates and Post-Delivery Material

1. \* Check all of the following categories that apply to this research:

45 CFR 46.204 Research involving pregnant women or fetuses.

45 CFR 46.205(a) and (b) Research involving neonates of uncertain viability.

45 CFR 46.205(a) and (c) Research involving nonviable neonates

45 CFR 46.205(d) Research involving viable neonates.

45 CFR 46.206 Research involving, after delivery, the placenta, the dead fetus, or fetal material.

45 CFR 46.207 Research not otherwise approvable which presents an opportunity to understand, prevent, or alleviate a serious problem affecting the health or welfare of pregnant women, fetuses, or neonates.

ID: HM20005575

[View: SF - Neonates: Viable \[45 CFR 46.205d\]](#)

## Neonates: Viable [45 CFR 46.205d]

If research data is collected on a neonate (newborn, after delivery) that is Viable, the regulations for special protections for children apply (Subpart D). Therefore, in addition to selecting Viable neonates here, Children must be selected in Study Population.

If research data is collected on pregnant women, or the viability of the neonate is questioned, other sections may apply.

ID: HM20005575

[View: SF - Potential Subject Identification and Recruitment](#)

## Potential Subject Identification and Recruitment

1. \* Choose all recruitment methods that may be used:

E-mail Campaign

Phone Solicitation

Flyers, Letters or Newspaper/TV/Radio Ads

 Website
 Direct Contact
 Psychology Research
 Participant Pool (SONA)
 VCU TelegRAM announcement
 Word of Mouth
 Other

2. If Other, please describe:

3. \* Select the methods used to obtain names and contact information for potential subjects:

 Pre-Existing Relationship with Participants
 Selected from Pre-Existing VCU Records
 Selected from Pre-Existing Non-VCU Records
 Selected from Publicly Available Records
 Referred by Health Care Provider or Other Health Professional
 Recruited from Database or Registry
 Identified through Community Based Organization (Schools, Church Groups, etc.)
 Self Referred (Flyer/Ad)
 Other

4. If Other, please describe:

5. \* Describe specific details for identifying and recruiting participants, including but not limited to:

- Specific locations where recruitment materials will be displayed
- How contact information is obtained for any direct contact with potential participants
- Who will approach and/or respond to potential participants:

Inpatient babies in the Neonatal Intensive Care Unit (NICU) will be screened for inclusion and exclusion criteria by investigators, who work in the NICU.

Families of potential subjects will be approached by one of the investigators for consent.

6. Describe any special recruitment procedures for vulnerable populations:

7. Upload all recruitment materials including ads, flyers, scripts, letters, email invitations, TelegRAM announcements, and postcard reminders:

8. \* Before potential participants consent to the study, will screening questions be asked or will any screening procedures/tests be done that would not otherwise be done as standard of care:

No

9. If Yes, will identifiable information about individuals be recorded during screening:

- Yes
- No

ID: HM20005575

[View: SF - Privacy](#)

## Privacy

1. \* Privacy is an individual's right to control how others view, record, or obtain information about them. When privacy is violated it can involve such things as being asked personal questions in a public setting; being publicly identified as having a particular characteristic or diagnosis; being photographed, videotaped or observed without consent; or disclosing personal information.

Describe how participants' privacy will be protected during:

- identification,
- recruitment,
- screening,
- the consent process,
- conduct of the study, and
- data dissemination:

The NICU is a single bed room design. All work including obtaining consent, and performing the study will be done in the private single bed room.

Data will only be reported in aggregate, not by individuals. No data will be linked to any information that could identify the subject

ID: HM20005575

[View: SF - Costs to Participants](#)

## Costs to Participants

1. Select all categories of costs that participants or their insurance companies will be responsible for:

 Participants will have no costs associated with this study
 Study related procedures that would be done under standard of care
 Study related procedures not associated with standard of care
 Administration of drugs / devices
 Study drugs or devices
 Other

2. If Other, explain:

3. \* Provide details of all financial costs to the participant, other than time and transportation. Additional details regarding standard of care costs will be requested on another screen, if applicable.

None

4. If applicable, upload a Cost Analysis form here:

ID: HM20005575

View: SF - Compensation

## Compensation

1. \* Describe any compensation that will be provided including:

- items such as parking/transportation
- total monetary amount
- type (e.g., gift card, cash, check, merchandise, drawing, extra class credit)
- how it will be disbursed:

None

2. If compensation will be pro-rated, explain the payment schedule:

ID: HM20005575

View: SF - Risks, Discomforts, Potential Harms and Benefits

## Risks, Discomforts, Potential Harms and Benefits

1. \* Describe the risks to participants associated with this study:

- physical, psychological, social, legal, financial, and other risks
- seriousness of given risks
- probability or likelihood of given risks

1. For some participants, the nasogastric tube may need to be replaced before the study begins. There is very very small risk of trauma,

bleeding or a transient drop in heart rate when a new tube is placed. Note that tubes are placed and replaced routinely in this population.

2. Even though both modes of non-invasive ventilation are currently used clinically, it is possible that one mode will not be as well tolerated as the other, or that it will take longer than one hour to adjust the settings. The subject might have more apnea/bradycardia/desaturation events. While these are common and are, in fact, why the patient is being treated clinically with one of the two modes under investigation, a significant increase in the events. If this occurs, the study will be stopped and the clinical team notified. Any needed interventions will be under the direction of the clinical team. The most likely outcome will be to place the subject back on the ventilation mode that he/she was on prior to the study.

3. The adverse events are the outcomes that will be affected by/measured for the interventions. Both NIPPV and NAVA are used to treat/prevent these events. The study is seeking to answer which mode is better at preventing them. Since we don't know this yet, it is possible that one of the modes will be worse, which is why it will be monitored as an adverse event, and if one mode does cause more events, the study will be stopped. Plus this info will be given to the clinician to use when selecting a mode for the patient in the future.

2. \* Describe how the risks / harms will be minimized:

1. The nasogastric tubes will be placed by experienced NICU personnel who place nasogastric tube every day.
2. The subjects will be monitored continuously by: cardiorespiratory monitor, 2 pulse oximeters and by direct observation by study personnel during the set-up phase and each four hour observations. If, during the first trial, the event number or severity increases beyond what would be considered safe in normal clinical care, the mode will be considered a failure. The clinical team will be informed and the clinical team (not the investigators) will decide if, in their judgment, the alternate mode should be used for the second trial. If the increased event number or severity occurs during the second trial, the mode will be considered a failure, the clinical team will be informed and the clinical team will determine further care decisions.
3. The events are ones that are monitored as part of the usual care, and this will continue during the study period. These babies are always connected to monitors which are linked to nursing phones as well as central telemetry. The investigator doing the study will be present to assess/intervene, and as back-up, the clinical team will provide their routine care for such events.

3. If the disclosure of any of the information obtained during the study would place the individual at risk for harm (legal, reputation, emotional etc.) and the information will be recorded so that the individual could be identified, explain the protections that will be put in place to decrease the risk of disclosure:

Not applicable

4. \* The Code of Virginia requires that most medical personnel and all employees of institutions of higher education report suspected child/elder abuse or neglect. Is it likely investigators could discover information that would require mandatory reporting by the investigators or staff:

Yes  
 No

5. \* Is it likely investigators could discover a participant's previously unknown condition (eg disease, suicidal thoughts, wrong paternity) or if a participant is engaging in illegal activities:

Yes  
 No

6. If yes, explain how and when such a discovery will be handled:

7. \* Describe any potential risks or harms to a community or a specific population based on study findings:

None anticipated

8. \* Describe criteria for withdrawing an individual participant from the study; such as safety or toxicity concerns, emotional distress, inability to comply with the protocol, etc.:

If, between consent and study, the subject no longer meets inclusion criteria or does not meet exclusion criteria.

If the number/severity of events becomes a clinically relevant safety concern, the study mode will be considered a failure. The clinical team will be informed and they will have the authority to stop the study.

9. \* Summarize any pre-specified criteria for stopping or changing the study protocol due to safety concerns:

The exact number/severity of events that might define a safety concern is subject dependent based on prior event history. A subject who normally has 0-1 events an hour may have a clinical safety concern at 4-5 events/hr while in one who is normally having 3-4 events/hr, the same rate of 4-5 events would not be significant. Clinically, a change in event rate is judged against baseline rate. However, events that require significant intervention, i.e. mechanical breathing support from ventilator or bag and mask, will be an absolute stopping indication.

The threshold for an adverse event will be dependent on the baseline level. If the baseline rate is, say, 4-6 events an hour, a 25% increase is 1 event, which is within the patient's variance. On the other hand, in one having no events, just one event is a 100% increase. We have 2 criteria - 1) An event that requires intervention with breathing support such as with more breaths or a bag and mask, 2) an increase from baseline of at least 4-5 events/hr. from baseline.

10. Where appropriate, discuss provisions for ensuring necessary medical, professional, or psychological intervention in the event of adverse events to the subjects:

Current protocols in place in NICU.

11. \* Describe any potential for direct benefits to participants in this study:

Observational results will be shared with the clinical team. These may include infant's comfort level on each mode of non-invasive ventilation; pressure levels on each mode, general frequency of apnea/bradycardia/desaturation events. Based on this information, the clinical team may choose to change the mode of ventilation.

There are no well-characterized tools to measure premature infant 'comfort'. There are semi-subjective pain scores that the nursing staff use but we are more likely to have irritation or discomfort from the probe. Thus, this will be an ongoing assessment of a) the infant's state - quiet sleep, quiet awake, agitated, restless, etc. b) new onset tachycardia or tachypnea coincident with applying the probes. c) facial grimaces that are different than baseline as assessed by the nurse caring for the patient.

12. \* Describe the scientific benefit or importance of the knowledge to be gained:

Information derived from analysis of study data may determine which mode of non-invasive ventilation is better in short term use for VLBW infants by examining outcome data with more depth and precision than is currently done clinically. This will help clinicians to better choose the optimal mode.

13. If applicable, describe alternatives (research or non-research) that are available to potential participants if they choose not to participate in this study:

They will be maintained on their current clinically chosen mode of ventilation

14. \* Indicate if this study will have a Data Safety Monitoring Board (DSMB) or a Data Safety Monitoring Plan (DSMP): [Required for all Full Review studies]

DSMB Review Required

DSMP Required

Not Required

ID: HM20005575

[View: SF - DSMP Details](#)

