
5. Moerer O, Beck J, Brander L, Costa R, Quintel M, Slutsky AS, et al. Subject-ventilator synchrony during neural versus pneumatically triggered non-invasive

**4. \* Briefly describe the study design, including all interventions or interactions with research participants and access to identifiable data. Use lay language whenever possible.**

STUDY DESIGN

a. Subjects

Subjects: VLBW (< 1501 grams birthweight) infants in the VCU Health System NICU who are receiving either NPPV or non-invasive NAVA therapy as ordered by their clinical providers. Investigators are clinicians who work in the NICU and will therefore be able to identify eligible subjects.

NAVA and NIPPV are different modes for the way non-invasive ventilation breaths are triggered. Both utilize the same delivery system, ventilator, cannula, etc. In NIPPV, the ventilator breaths are triggered by time, i.e. the ventilator sends a breath to match the prescribed rate like one every 3 seconds for a rate of 20 breaths per minute, no matter whether the patient is inhaling or exhaling. In NAVA, the normal feeding tube is replaced by a special tube that has a sensor located around where the diaphragm surrounds the esophagus. The sensor picks up the electrical signal of the diaphragm muscle contracting, and this mark of the beginning of inhalation is used to trigger a machine breath, so the machine and the patient are coordinated. Aside from the catheter connection, all other procedures are the same.

b). Randomization - the order of modes will be assigned based on a random number table using a 5 block design to match the DSMB reporting needs. c) The change from one mode to the next involves activating a switch on the ventilator. There are no procedures that need to be done to the subject. They will remain in their current environment, connected to all the routine and study-related monitoring equipment. d) During the study, which involves both modes, the subjects will be monitored as routine by the staff, as well as one of the study faculty ([name] or [name]). In the event that one of us needs to step away briefly, an attending neonatologist and a neonatal fellow are on site in the NICU

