## Study Population

1. \* Provide the total number of participants you expect to enroll in this study under the VCU IRB:  
15

2. If this is a multi-Center Project, what is the total anticipated number of subjects across all sites:

3. \* Provide justification for the sample size:

Sample Size

Based on published data, monitored events occur at an average frequency of 9.2 over a 4-hour period. The degree of variability is not known but assuming an SD of 50%, a sample size of 10 subjects would have an 0.8 power for a 50% reduction in events at an alpha of 0.05. A similar study to ours comparing NIPPV and flow-synchronized NIPPV (2) had 19 participants and achieved statistically significant differences between the two modalities. Based on this, we are anticipating a need for 15 subjects

4. \* List the study inclusion criteria:

1. < 1501 grams (VLBW infant)
2. Patient must be receiving daily caffeine therapy for apnea
3. On non-invasive ventilation, either NIPPV or non-invasive NAVA

5. \* List the study exclusion criteria:

1. No concerns for acute sepsis (i.e., blood cultures, if drawn, have been negative for 48 hours, and no active signs/symptoms of sepsis).
2. No history of meningitis or seizures
3. No signs of increased intracranial pressure, including bulging fontanelle, presence of ventricular shunt device, or ventriculomegaly by most recent ultrasound.
4. Presence of Grade III or IV intraventricular hemorrhage
5. No cyanotic heart defects or clinically significant congenital heart disease. Will allow PDA, PFO, and mild to moderate ASD/VSD as determined by pediatric cardiology.
6. Non-English speaking legal representatives (parents)

6. \* Check all participant groups that are likely to be involved in this study. If it is possible that a regulated vulnerable population (children, pregnant women, prisoners) COULD BE involved in the study, be sure to check them:

Healthy Volunteers

Children

Emancipated Minors

Pregnant Women

Fetuses, Neonates, Fetal Material or In-Vitro Fertilization

Prisoners

Decisionally Impaired Adults

When cancer is integral to the research - cancer Patients, Family Members, Healthcare Providers or Prevention

VCU Health System Patients

Non-VCU Patients

VCU/VCUHS Students or Trainees

VCU/VCUHS Employees

Individuals with Limited English Proficiency

Active Military Personnel

When researching in a K-12 environment - populations Within School Districts or Other Learning Environments

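### The rate-based adverse event is a rise over the infant's own history, so its count depends on which mode infants entered on and cannot alone show that one mode is worse

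*Combined protocol and SAP*

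**What the plan says.** All references are to the combined protocol and SAP.

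- **Criterion.** Risks, Discomforts, Potential Harms and Benefits, item 9, gives two adverse-event criteria. The first is an event needing breathing support. The second is "an increase from baseline of at least 4-5 events/hr. from baseline". The same item calls the level of concern "subject dependent based on prior event history" and adds: "Clinically, a change in event rate is judged against baseline rate". No baseline period, baseline mode or averaging window is given.
- **Failure label.** Item 2 of that section calls a mode a failure when event number or severity increases beyond what is safe in normal care. Item 9 ties safety concern to the infant's history.
- **Purpose.** Item 1, point 3: "it is possible that one of the modes will be worse, which is why it will be monitored as an adverse event".
- **Entry mode.** Research Description, item 4, describes infants "who are receiving either NPPV or non-invasive NAVA therapy as ordered by their clinical providers". The matching inclusion criterion in Study Population, item 4, is: "On non-invasive ventilation, either NIPPV or non-invasive NAVA". No quota or stratification by entry mode is stated.
- **Randomisation.** Only sequence is randomised: "the order of modes will be assigned based on a random number table using a 5 block design". Every infant is recorded for 4 hours on each mode, so one session continues the entry mode and the other is a switch.
- **Reporting.** DSMP Details, item 1, sends failures, event frequency and severity, outcomes and adverse-event data to one safety reviewer every 5 infants. That reviewer's opinion on continuing is final. No split by study mode or entry mode is described.

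**The concern.** A rise over baseline measures the change caused by taking part in the study. It does not measure how good or bad a mode is. If an infant's recent history was recorded on NIPPV, any harm from NIPPV is already in the baseline. The NIPPV session is then expected to show no rise, and only the NAVA session can. For an infant who entered on NAVA the reverse holds.

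The protocol itself describes the case that this misses. Research Description, item 4, worries about an infant who has far more events on the clinician's chosen mode than on the alternative. Criterion 2 would not be expected to flag that infant: the poor mode supplies the baseline, and the other mode shows a fall. The bedside clinician is to be given the counts in that situation, but the safety-report text contains no matching comparison by mode.

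At stake is how the safety reviewer reads the adverse-event and failure counts. If most infants entered on the harmful mode, few rises would be counted against it, and the count could look reassuring for a reason unrelated to safety. In groups of 5 infants the entry mix can easily be uneven.

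**Working it through.** **1. The plan's own figure, which supplies the planning effect.** Study Population, item 3, gives a mean of 9.2 events per 4 hours, an SD of 50% (4.6), a 50% reduction (4.6), alpha 0.05, n = 10 and power 0.8. Reading 4.6 as the SD of the within-infant difference, the standardised difference is 4.6/4.6 = 1. A two-sided paired t-test with n = 10 then has power 0.803, so the stated 0.8 is reproduced. Per hour, the planning rates are 9.2/4 = 2.3 and 2.3 × 0.5 = 1.15, a gap of 1.15 events/hr.

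**2. The expected rise.** Let an infant's event rate be a on the entry mode and b on the other mode. If the baseline comes from the entry mode:

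- studied on the entry mode, expected rise = a − a = 0;
- studied on the other mode, expected rise = b − a.

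The first result holds for any value of a.

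**3. Probability of meeting criterion 2.** The documents do not give the size of harm, the baseline period, the variation between infants or the window, so these are assumptions: Poisson counts, a 24-hour baseline on the entry mode, a threshold of 4 or 5 events/hr, and the rise read either on the 4-hour average or in any single hour. The harmful mode runs at 2.3 + 4.5 = 6.8/hr and the other at 2.3/hr. CV is the between-infant coefficient of variation. For 15 infants, with k having entered on the other mode:

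expected count on the harmful mode = k × P(after switch) + (15 − k) × P(entry mode)

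| Harm | CV | Threshold, window | P after switch | P if entry mode | Count, k = 12 | Count, k = 3 |
|---|---|---|---|---|---|---|
| +4.5/hr | 0 | 4, 4-h average | 0.641 | 0.004 | 7.7 | 2.0 |
| +4.5/hr | 0.5 | 4, 4-h average | 0.515 | 0.006 | 6.2 | 1.6 |
| +4.5/hr | 0 | 5, 4-h average | 0.352 | 0.001 | 4.2 | 1.1 |
| +4.5/hr | 0 | 4, any hour | 0.954 | 0.267 | 12.2 | 6.1 |
| +4.5/hr | 0 | 5, any hour | 0.861 | 0.148 | 10.8 | 4.4 |

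First row written out: 12 × 0.641 + 3 × 0.004 = 7.7, and 3 × 0.641 + 12 × 0.004 = 2.0. The harm is the same in both; only the entry mix differs.

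**4. At the planning effect (1.15 against 2.3/hr).** On the 4-hour average the probability is at most 0.012 even after a switch, so at most 15 × 0.012 = 0.18 expected events in the whole trial. If any single hour counts (threshold 4, CV 0.5), it is 0.200 after a switch and 0.060 on the entry mode, giving counts of 2.6 (k = 12) and 1.3 (k = 3).

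**5. Direction.** In the first row the criterion is met on the other, better mode with probability about 0 for either kind of entrant. Under the single-hour reading (threshold 4, CV 0) it is 0.051 for infants who entered on that mode and 0.0001 for those who did not. So the entry mix changes how strongly the harm shows. It does not move the excess to the better mode.

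**The case against.** **What stands.**

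- The safety reviewer also receives outcomes and event frequency and severity. The primary outcome compares event counts by mode, with each infant recorded on both. Those data do not use the baseline, so harm is not hidden from all review.
- The breathing-support criterion does not depend on baseline either.
- As a bedside rule, criterion 2 is coherent. Outside the study the infant would stay on the entry mode, so a rise over that state is the risk added by taking part.
- That the baseline was recorded on the entry mode is inferred. Consent Groups notes that these infants usually stay for weeks, so their history could span both modes or other support.

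**Stronger readings that the documents do not support.** A reader might infer that:

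- *The whole adverse-event tally follows the entry mix.* Only its rate-based part does, and probably the failure label.
- *A mode can produce these events only in infants who entered on the other mode.* That is true of the expected rise, not of every event. Under a single-hour reading, chance rises on the entry mode are not negligible (0.15 to 0.27 in the table).
- *The plan divides each mode's count by all 15 infants.* No denominator is planned.
- *The count would blame the better mode, or show a large imbalance between equally harmful modes.* With one mode truly worse, step 5 shows no such reversal. Equal event rates in each infant would give no expected rise on switching. An imbalance would need switching itself to provoke events, or opposite responses in different infants, and the documents argue neither.

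**What does not stand.** The comparative reading is not invented. Item 1 of the Risks section states that purpose, and failure counts go to a reviewer with the final say.

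**Conclusion.** The point holds in a limited form. If the baseline is mostly entry-mode history, criterion 2 has an expected rise of about zero on the entry mode. The rate-based adverse-event count, and probably the failure count, then depends on the entry mix and cannot on its own fairly show whether one mode is worse. The effect is a loss of sensitivity to harm from the mode on which most infants entered.

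The size rests on assumptions that the documents do not supply. It is large for a harm of +4.5 events/hr (an expected count of 7.7 or 2.0, depending on entry mix, on the 4-hour average with threshold 4). It is negligible on that average at the planning effect. The entry split, baseline period and averaging window are all unstated. The primary analysis, the raw event frequencies and the breathing-support criterion are unaffected. Severity: minor, a free improvement.

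**What to change.** Leave the bedside rule and its thresholds unchanged.

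1. In DSMP Details, item 1, have each 5-infant report show adverse events and failures by study mode and by whether that mode was the infant's entry mode, with the number of infants in each of the four cells.
2. In the same report, list each infant's two study-period event rates side by side, with hours recorded. Mark any session that was cut short or not done, since the Risks section allows the study to end after a failure; such infants have no complete pair and must be read from the first table.
3. In the Risks section, item 1, point 3, state that whether one mode is worse is judged from this within-infant comparison and not from the rise over baseline.

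The cost is one table, one listing and a few sentences. Pre-study ventilator settings (Research Description, item 4) and ventilator mode (HIPAA, item 1) are already collected, so no new data are needed.
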